Appendix 2. Infusion Related Reactions

For defining an AE as IRR the onset of the event in relation to the infusion of study drug and time to resolution of the event will be considered.

- All AEs identified by the MedDRA PT query describing signs and symptoms will be considered potential IRRs when onset is on the day of study drug infusion (during or after infusion) and the event resolved with end date within 2 days after onset.
- All AEs identified by the MedDRA PTs of Infusion related reaction, Drug hypersensitivity, Anaphylactic reaction, Hypersensitivity, Type 1 hypersensitivity, will be considered potential IRRs when onset is on the day of study drug infusion (during or after the infusion) or the day after the study drug infusion (irrespective of resolution date).

The list of MedDRA PTs for ‘IRRs SIGNS and SYMPTOMS’ and PTs ‘IRRs CORE’ are defined in the SRP for avelumab.

Infusion-related reactions (IRRs) will be programmatically identified as outlined in Table 12 and will be identified for IV drugs only.

Table 12. Case Definition for IRRs – IV Study Drugs Administered Alone Or In Combination With Non-IV Study Drugs

Condition	Selection criterion
If AE meets [1 AND 2] OR [3 AND (4A OR 4B)] then AE is classified as an IRR	
1	PT is included in the ‘IRRs SIGNS and SYMPTOMS’ list
2	
 • AE onset date = date of infusion of study drug AND • AE timing related to study drug (‘DURING’, ‘AFTER’) AND • AE outcome in (‘RECOVERED/RESOLVED’, ‘RECOVERED/RESOLVED WITH SEQUELAE’, ‘RECOVERING/RESOLVING’) AND • AE end date – AE onset date <=2
3	PT is included in the ‘IRRs CORE’ list
4A	
 • AE onset date = date of infusion of study drug AND • AE timing related to study drug in (‘DURING’, ‘AFTER’)
4B	AE onset on the day after infusion

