6.6.4. Other Significant Adverse Events

The frequency (number and percentage) of patients with each of the following will be presented for irAEs, by treatment group:

- irAEs leading to death, by Cluster and PT;
- irAEs, by Cluster and PT;
- irAEs, Grade ≥ 3 , by Cluster and PT;
- irAEs leading to discontinuation of avelumab, by Cluster and PT;
- irAEs leading to discontinuation of axitinib, by Cluster and PT;
- irAEs leading to discontinuation of any study drug, by Cluster and PT;

- irAEs leading to discontinuation of all study drugs, by Cluster and PT;
- Serious irAEs, by Cluster and PT.

The listing of all irAEs will also be provided with the relevant information with a flag for irAEs with onset outside of the on-treatment period.

The frequency (number and percentage) of patients with each of the following will be presented for IRRs, by treatment group:

- IRRs leading to death, by PT;
- IRRs, by PT;
- IRRs, Grade ≥ 3 , by PT;
- IRRs leading to discontinuation of avelumab, by PT;
- Serious IRRs, by PT;
- Time related to first onset of an IRR (infusion 1, infusion 2, infusion 3, infusion 4 or later).

The listing of all IRRs will also be provided with the relevant information with a flag for IRRs with onset outside of the on-treatment period.

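### A fatal reaction recorded only by a symptom term cannot be classed as an IRR under Table 12, so a zero in the fatal-IRR table would not rule one out

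*SAP*

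**What the plan says.** SAP Appendix 2 states that "Infusion-related reactions (IRRs) will be programmatically identified as outlined in Table 12". The table's rule is: "If AE meets [1 AND 2] OR [3 AND (4A OR 4B)] then AE is classified as an IRR". That gives two routes.

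- **Symptom route (conditions 1 and 2).** Condition 1 is that "PT is included in the ‘IRRs SIGNS and SYMPTOMS’ list". Condition 2 then requires all of the following: onset on the day of infusion, timing during or after the infusion, "AE outcome in (‘RECOVERED/RESOLVED’, ‘RECOVERED/RESOLVED WITH SEQUELAE’, ‘RECOVERING/RESOLVING", and "AE end date – AE onset date <=2". The text above the table says the same in words: "the event resolved with end date within 2 days after onset".
- **Core route (conditions 3 and 4A or 4B).** The text names five diagnostic terms: infusion related reaction, drug hypersensitivity, anaphylactic reaction, hypersensitivity and type 1 hypersensitivity. Only timing is tested: onset on the infusion day "or the day after the study drug infusion (irrespective of resolution date").

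SAP 3.5.1 makes IRRs an adverse event of special interest. SAP 6.6.4 plans, among the IRR summaries, "IRRs leading to death, by PT". SAP 6.1.1.1 includes Section 6.6.4 in the analysis of the primary endpoint. SAP 6.6.1 defines an adverse event leading to death by a fatal outcome or Grade 5.

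**The concern.** For a symptom-coded event, the outcome that would place it in the fatal-IRR table is the outcome that stops it from being an IRR at all. The table would then show zero for such events whether or not one had occurred, and a reader of the study report could not tell which.

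Symptom coding is not far-fetched. Protocol 5.4.5.5 describes these reactions through symptoms such as hypotension, dyspnoea, wheezing and urticaria, and the SAP has a symptom route because some reactions are expected to be recorded that way.

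The same IRR flag feeds the overall adverse event summary (SAP 6.6.1.1), the Grade 3 or higher and serious IRR tables (SAP 6.6.4), and IRRs by anti-drug antibody status (SAP 6.2.5.3). A fatal case would drop out of each of these that it should have entered. Safety is the primary objective, so the meaning of a zero matters even in a small study.

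**Working it through.** The plan gives no figure on this point, so there is none to reproduce. The check is one of logic: write Table 12 as a yes/no rule and run every combination through it.

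**Inputs**

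- From Table 12: the two routes, the three accepted outcomes, the onset and timing tests, and the limit of 2 days from onset to end date.
- Assumed: the form also offers not recovered, fatal and unknown as outcomes. The SAP does not list all the categories, although SAP 6.6.1 does refer to a fatal outcome.

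**Grid for each list and outcome**

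Onset on the infusion day or the next day (2) × timing during or after (2) × days from onset to end date of 0, 1, 2, 3 or missing (5) = 2 × 2 × 5 = 20 combinations.

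**Symptom route**

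For an accepted outcome, the rule passes infusion-day onset only (1), either timing (2) and 0, 1 or 2 days (3): 1 × 2 × 3 = 6. For any other outcome the outcome test fails first, so none pass.

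**Core route**

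Condition 4A passes infusion-day onset: 2 × 5 = 10. Condition 4B passes next-day onset: 2 × 5 = 10. The total is 10 + 10 = 20, whatever the outcome.

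| Term list | Outcome | Classified as IRR |
|---|---|---|
| Symptom | each of the three recovered or recovering outcomes | 6 of 20 |
| Symptom | fatal | 0 of 20 |
| Symptom | not recovered | 0 of 20 |
| Symptom | unknown | 0 of 20 |
| Core | any of the six, including fatal | 20 of 20 |

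These are counts of rule combinations, not probabilities.

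**Consequence for the planned table**

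An entry must be both an IRR and fatal. For symptom terms the overlap is empty; for core terms it is not. So the table can be filled only through core terms.

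**After the change proposed below**

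With a fatal outcome accepted and days counted from onset to death, the symptom route passes 1 × 2 × 3 = 6 of 20 fatal combinations, the same as for recovered events. A death 3 or more days after onset still fails.

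**Size in one case**

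With 20 patients, one such event is 1/20 = 5%, shown as 0/20 = 0%. This illustrates the effect of a single case and does not estimate how often it would happen.

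**The case against.** **The core route catches the likely cases.** The core terms are the diagnoses an investigator would probably record for a suspected fatal reaction, and Protocol Tables 2 and 3 treat infusion-related reaction as a named toxicity with its own grades. This stands as a limit on reach. It does not close the gap, because nothing in the documents requires a core term to be used.

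**The death is not hidden.** An event starting on an infusion day falls in the on-treatment period unless a new anti-cancer drug had already started. A fatal one appears in the tables of treatment-emergent events leading to death (SAP 6.6.1.1), among serious events (SAP 6.6.3), and in the death listing with the fatal terms beside the last dosing date (SAP 6.6.2). With about 20 patients it would be seen case by case. No hypothesis test or decision rule uses the IRR table (SAP 5.1). All of this stands.

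**Quick resolution is there for a reason.** It separates a reaction from an unrelated symptom on the same day. In advanced liver cancer, a symptom followed by early death may have another cause. This stands too, and is why the remedy needs a review step as well as a wider outcome list.

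**The text speaks only of potential IRRs.** That could suggest a later review. Table 12, however, classifies the event outright and by program, and Appendix 2 has no counterpart to the closing paragraph of Appendix 1, which lets medical review refine the immune-related events. This objection does not stand.

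**Stronger readings that the documents do not support**

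- A reader might infer that the table misses every fatal IRR. It does not: core terms pass whatever the outcome.
- A reader might size the problem from Protocol 1.2.4, where 7 of 47 patients had an IRR and 1 of 47 a Grade 3 IRR. Those figures appear to count the reported term infusion-related reaction, which is a core term that condition 2 does not touch. The one Grade 5 event there was myocarditis. No rate for symptom-only reactions is given.
- A reader might conclude that IRR severity is biased downward throughout. Condition 2 does also drop symptom events that are unresolved or last more than 2 days, but Appendix 2 says that time to resolution is part of the definition. The contradiction with a planned table is specific to fatal events.

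**Conclusion.** The point holds as a narrow defect of classification. As written, an infusion-day reaction recorded only by a symptom term and ending in death cannot be an IRR, and a zero in the fatal-IRR table does not exclude one. What is lost is the IRR label, not the death.

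The expected numerical effect is small and cannot be estimated from the documents. The change is worth making because it is cheap and the table belongs to the primary safety analysis, not because a case is likely.

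The conclusion rests on three assumptions:

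- A fatal reaction is recorded with a fatal outcome. A Grade 5 record entered as recovered could pass, but that would be a data error.
- The symptom term is not also on the core list. Both lists are in the Safety Review Plan, which is not among the documents. A term on both would pass by the core route.
- No medical review of IRRs is laid down elsewhere, for example in that same plan.

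**What to change.** Make three edits to SAP Appendix 2 before database lock.

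1. **Table 12, condition 2.** Add fatal to the accepted outcomes. For fatal events, replace the end-date test with death date minus onset date of at most 2 days. Using the death date also covers fatal records with no end date. State whether a death date imputed under SAP 5.3.3.2 may be used.
2. **Appendix 2 text.** Change the matching sentence on symptom terms so that it allows an event that either resolved or was fatal within 2 days of onset.
3. **Medical review.** Add for IRRs the provision that Appendix 1 has for immune-related events. Review can then remove a fatal case with a clear other cause and add cases the program missed, including a death 3 or more days after onset. Keep a record of each change and its reason.

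**Cost.** A few lines of SAP text, a small program change and review of probably very few cases. It needs no new data collection: outcome, onset date and death date are already planned. There is a small downside: until reviewed, an unrelated early death after a same-day symptom could be flagged as an IRR, and in 20 patients one false flag would show 5% in place of 0%. The third edit is there to limit that risk.
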